## **9. Privacy, Confidentiality, and Data Security**

*Privacy.* Among the study team are four members tasked with data management, [name], ORPRN program manager, will oversee the REDCap project (i.e., database). [name], project director, will build and manage the Practice Member Questionnaire on Qualtrics for data collection. [name] and [name] will share the data with [name], MS, a biostatistician, who will manage data from the chart audits and surveys for analysis. [name], a qualitative analyst, who will manage the data from qualitative interviews. REDCap and Qualtrics offer controlled user access, which allows [name] the ability to provide completely anonymized or deidentified data. OCTRI's REDCap software is housed on servers located in ITG's Advanced Computing Center providing locked physical security. Qualtrics' servers are protected by high-end firewall systems audited using an industry standard (i.e., SSAE-18 method).

[name] will remove PHI from chart audits and survey data. Additionally, she will perform data quality control checks and implement cleaning procedures. Data will be stored on a secure, password-protected network at OHSU. [name] will also remove PHI field notes from observations and interview data. All study team members are highly trained and appropriately certified in confidentiality, data security and the current protection measures represent the cutting edge of electronic protection. [name] will also store data on a secure, password-protected network at OHSU.

*Confidentiality.* Many safeguards are in place to protect the ORPRN data. All data from the practice sites will be stored on secure servers at ORPRN. ORPRN staff will remove all personal identifiers from the charts and will assign each patient a unique identification number. ORPRN staff work with patient data from their member clinics on a regular basis and are appropriately trained in data security. Limited data will only be shared by ORPRN practice sites with OHSU once memorandums of understanding are fully executed.

Analysts will maintain the analytical data file for a period of two years following the end of the study period to permit appropriate ongoing analysis. After two years from the study conclusion date, the files will either be destroyed, or will be used for ongoing research. In the latter instance, [name] will file a new application for IRB approval. The protocol and procedures for using the data ensures no patients are individually identifiable during data transfers and analyses. We have previous experience in conducting these types of data transfers and data sharing between OHSU and ORPRN. All research staff are highly trained and appropriately certified in data security and confidentiality, and the current protection measures represent the cutting edge of electronic protection.

*Data Security.* The proposed study includes two teams, quantitative and qualitative, managing outcome data. All of the qualitative data collected (i.e., site observations and interviews) will be securely managed by [name] under the direct supervision of [name]. [name] will manage and coordinate the sending and receiving of qualitative study data using strict HIPAA compliant procedures. Under the direction of [name], co-investigator, a biostatistician, [name], will securely manage all chart audit and survey data from ORPRN practice sites. Chart audit and survey data will be securely collected and transferred to OHSU, and quality control checks will be performed. For chart audits, OHSU will work in collaboration with [name]

[name], ORPRN practice facilitator. [name] will participate in weekly meetings with the quantitative team to review data quality and to make decisions about included data. In addition, OHSU and ORPRN will follow a four-part data quality monitoring procedure consisting of using a standardized abstraction protocol, extensive training, monitoring of Kappa values between abstractors, and continuous quality improvement through feedback. For surveys, [name] will work with [name], ORPRN program manager, to securely access survey data from REDCap. The REDCap servers are housed behind both the OHSU firewall and a second ACC firewall. All transmissions of data from the application are encrypted over HTTPS with the industry standard TLS 1.1 protocol (AES 256-bit encryption). To maintain data integrity, REDCap is jointly managed in accordance with OHSU Information Security Directives by ACC staff and members of OCTRI's Biomedical Informatics Program, ensuring fidelity of database configuration and back-ups. User activities are logged to enable auditing of all data changes. Qualtrics services are hosted by trusted data centers, which are audited using the SSAE-18 method. Additionally, Qualtrics is ISO 27001 certified and is FedRAMP authorized, which is considered a gold standard of security certification used by U.S. federal government. Qualtrics also possesses a HITRUST certification for compliance with HIPAA.

OHSU and ORPRN have both standard and Internet 2 connectivity through a link to Seattle's Pacific Northwest Gigapop. Its IP network is based on meshed switched gigabit ethernet with distributed routing, with 100 Mbps to the desktop. The network can be accessed via standard TCP/IP or Novell Netware. OHSU's Information Technology Group (ITG) supports both Windows and MAC workstations for OHSU personnel. It also maintains web and application server clusters for application hosting and MS SQL Server and Oracle database servers for departmental use, including support for SSL communications and databases optimized for security of protected health information. Secure communications by electronic mail are also provided using Tumbleweed Secure messaging software. In addition, all data will be computerized and managed on OHSU and ORPRN HIPAA-compliant computers. All data will be stored and backed up password-protected secure servers.

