## iv. **Setting**

ORPRN is a statewide practice-based research network of primary care providers, community partners, and academicians dedicated to studying health care delivery and how to improve the health of Oregonians and to reduce health disparities. ORPRN works with 279 primary care practices, including 51% that are rural and 42% provider-owned. Practices have participated in studies related to care delivery redesign, heart health, cancer prevention, and social

determinants of health. ORPRN is organized into regions, each served by a facilitator that supports improvement initiatives and collects research data.

v. **Recruitment Methods**

ORPRN's experienced recruiters will personally contact practices through a faxback process to assess interest, capacity and eligibility. ORPRN will distribute a recruitment flyer to its network of primary care practices, detailing the purpose of the study, eligibility requirements, as well as responsibilities of participating practices. Interested sites will submit a non-binding agreement to ORPRN to participate in the pilot study, either by fax or email. ORPRN and the study team will select four practices.

INTEGRATE-D aligns with programs relevant for practices in the Northwestern region (e.g., CPC+; Accountable Care Organization changes) and recruiting should not pose a challenge. Practices that agree to participate must sign a Memorandum of Understanding outlining expectations and responsibilities for participation. To encourage practice member participation, full explanation of the study and the purpose of the data collection activities will be given to practice members by the study team. For patient participation in interviews, the study team will work with a practice liaison, who will make the first contact with patients to ascertain permission to be contacted by a study member. The research team will contact them to explain the study, review the consent information sheet, and provide details of the interview. Patients will receive compensation in the form of a \$25.00 gift for their participation. Patients will be informed that the interviews are entirely voluntary. A patient sample will be drawn from the chart audits. Medical records are a secondary analysis of existing data; therefore, the study team will not recruit or seek consent from patients for the chart audits.

vi. **Consent Process**

*Modifications to the Consent Process*

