**Table 1. Data Collection Timeline**

Data Collection Activities	Year 1				Year 2			
	1	2	3	4	1	2	3	4
Quarter								
Semi-Structured Interviews								
Direct Observations (i.e., Site Visit Observation Guide)	X B						X F	
• Pre-Site Visit Interview	X B							
• Practice Member Staff Interviews	X B						X F	
• Interim Interviews	X	X	X	X	X	X		
• Patient Interviews							X F	
Survey Administration								
• Practice Survey			X B				X F	
• Practice Member Questionnaire			X B				X F	
Chart Audits								
• Test Chart Audits					X			
• Conduct Chart Audits							X	

*Qualitative Methodology.* The procedures for qualitative and quantitative approaches are documented as follows.

- Primary Care Practices.* In Year 1, quarter 1, the study team will randomly assign the four primary care practices to an experimental condition (i.e., treatment and control group). Following the assignments, in Year 1, quarter 3 the study team will conduct semi-structured interviews with staff at all four practices. Originally, the study team proposed site visit observations; however, due to COVID-19, semi-structured data collection will occur by phone or via web-conferencing software (i.e., Cisco Webex). Follow-up interviews will occur 15 months, post-intervention.

During the semi-structured interviews, study team members will take notes. Neither protected health information (PHI) nor identifiers will be recorded. Field notes will be prepared within 24 hours of the site visit's end. All notes will be de-identified and destroyed after the full field notes are prepared.

After the baseline interviews, the study team will also conduct interim interviews with one point of contact from each practice implementing INTEGRATE-D. The interviews will be 30- minute monthly check-in phone calls to minimize recall bias and gather real-time experiences with INTEGRATE-D. The audio recordings will be professionally transcribed, checked for accuracy and de-identified.

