#### *Quantitative Methodology*

- i. *Chart Audits.* The study team will conduct virtual chart audits all four primary care practices (80 individuals per practice). The data will measure key behavioral health (i.e., depression), DMII process (i.e., self-management activities). The study team will conduct the audit, pre- intervention for a baseline, and 15 months post-intervention for follow-up. As noted earlier, chart audits are a secondary analysis of existing data; therefore, the study team will not recruit or seek consent from patients for the chart audits.
- ii. *Surveys.* The study team will administer two surveys during the study.

The first of which is a Practice Survey. One practice staff person (e.g., office manager, clinical lead) will complete this survey for each practice. The Practice Survey collects demographic data (e.g., ownership) and include items from the Change Process Capability Questionnaire to measure quality improvement strategies the practice uses. The survey will be administered online through RedCap.

The Practice Member Questionnaire will be administered online via Qualtrics to a select number of staff. We will ask the office manager for each practice to provide a list with employees' names, role and email addresses. The study team will use a stratified random process to select staff who will receive a survey. Staff who are selected will receive an email invitation from us to complete an anonymous online survey. We anticipate that there will be 10-15 practice members asked to complete this survey at each practice, but this will vary based on practice size and diversity of team roles. Due to COVID-19, the study team altered its initial approach, which would have taken place at an in-person all-staff meeting to collected baseline and follow-up data. For now, we are altering baseline data collection only.

For the initial submission, the study team is submitting for approval of the following qualitative and quantitative measures at baseline: the Pre-Site Visit Interview Guide, Site Visit Observation Guide, Practice Member Staff Interview, Patient Interview, Practice Survey, and Practice Member Questionnaire. As the study team refines the intervention, modifications to the IRB will be submitted.

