**Table 1. Intervention Components, Description, Frequency and Timeline**

Intervention Component	Who Provided Support	Description	Frequency and timeline
Expert Training	Physician, BHC, and expert in implementing DD	Education for clinical teams in ADA recommendations and self-management support materials  1.Psychosocial care, type 2 diabetes and DD training for all clinical roles delivered by a physician and DD expert 2.BHC training about the role of the BHC in caring for patient with type 2 diabetes delivered by a clinical	IC1 received these remotely March and May 2021  IC2 was given a recording of these trainings. We do not

		psychologist with expertise in integrated behavioral health and primary care	know if these were reviewed by IC2.
Facilitation	Practice Facilitator	
Customized remote once-a-month meetings with an experienced practice facilitator using Bodenheimer's Building Blocks framework utilizing Plan Do Study Act (PDSA) cycles. Meeting topics were tailored to the clinic's experience and aligned with ADA recommendations and included:
 
 
• Patient education materials for BH and self-management support
 
• Implementation of systematic screenings for DD, depression, anxiety
 
• Identifying changes in roles/responsibilities, new processes/workflows for screening and treatment
 
• Identify cross-functional practice team, train team in QI
 
• Proactive outreach to patients regarding DMII, self-management status, community and family needs
 
• Pre-visit planning and huddling, scheduling BHC visits with warm handoffs
 
	IC1: December 2020-February 2022 IC2: June 2021-May 2022

IC=Intervention Clinic; BHC=Behavioral Health Clinician; DD=Diabetes Distress; QI=Quality Improvement; DMII=Type 2 Diabetes Mellitus; ADA=American Diabetes Association

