## ***Data Collection***

We evaluated quantitative data 12 months before the first facilitation visit (pre-intervention) to six-months after the last facilitation visit (post-intervention). Pre-intervention interviews and survey data were collected between November 2020 and July 2021. We delayed the intervention start for Intervention Clinic 2 (IC2) to allow them to prioritize their COVID response, adjusting data collection for IC2 and its matched control clinic 2 (CC2). Monthly check-in calls with ICs started in the month following the first intervention visit (December and June, respectively) and continued for the duration of the intervention. Post-intervention survey and interviews were conducted between March and June 2022 for IC1 and between June and July 2022 for IC2.

Survey data. We conducted two surveys. One was completed by the office manager or clinical leader from each clinic (N=4). This survey collected clinic demographic data and 14 items from the Change Process Capability Questionnaire (CPCQ), which was modified to assess a medical groups use of quality improvement strategies aligned with improve type 2 diabetes care.

Demographic data were collected once, pre-intervention. The CPCQ was completed pre- and post-intervention (see Appendix 2). ICs and CCs completed this survey with a 100% response rate. The second survey assessed the feasibility, acceptability and appropriateness of INTEGRATE-D using three psychometrically assessed measures developed by Weiner et al. This survey was distributed to clinical team members exposed to the intervention (N=17) after the intervention ended, with an 82% response rate. Surveys were conducted using REDCap.

EHR data. EHR data were abstracted through a combination of manual and automated reporting, both of which followed a protocol. Research staff assisted clinic staff with creating a list of patients with type 2 diabetes seen in the clinic at least once in the 15 months prior to the

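### A practice facilitator appears to share in chart-data inclusion decisions after randomisation, with no masking to arm described; keep intervention facilitators out of those decisions and report who made them

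*Protocol*

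**What the plan says.** Protocol section 9 (Data Security) introduces the chart-audit collaborator with "For chart audits, OHSU will work in collaboration with", followed by a removed name described as an ORPRN practice facilitator. The next sentence, whose subject is also a removed name, says that the person "will participate in weekly meetings with the quantitative team to review data quality and to make decisions about included data". The paragraph then lists four quality measures (a standard abstraction protocol, training, Kappa monitoring between abstractors, and feedback) before it turns to surveys. The same section says that a biostatistician "will securely manage all chart audit and survey data from ORPRN practice sites".

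On timing, Protocol section 6 states: "In Year 1, quarter 1, the study team will randomly assign the four primary care practices to an experimental condition". Its chart-audit paragraph gives a pre-intervention baseline audit and a second audit "15 months post-intervention for follow-up".

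On delivery of the intervention, SAP Table 1 lists a practice facilitator as provider of the facilitation component, described as "Customized remote once-a-month meetings with an experienced practice facilitator". The Setting paragraph of Protocol section 5 says that ORPRN is organised in regions, "each served by a facilitator that supports improvement initiatives and collects research data".

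The SAP's Data Collection section describes EHR collection in the past tense. It says "Research staff assisted clinic staff with creating a list of patients with type 2 diabetes seen in the clinic at least once", and it names trained audit staff for the chart work. The facilitator appears there only as the author of session notes and as a party to monthly check-ins with the study team.

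**The concern.** Someone who helps a clinic to improve its screening has a natural interest in that clinic's screening record and knows which arm it is in. If that person also helps to decide which chart data count, a borderline record could be kept or dropped with the arm in view. This need not be deliberate.

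The outcomes exposed are those taken from charts: A1C, cholesterol, nephropathy and psychosocial screening, and the A1C and PHQ-9 values. They include the process-of-care metrics of the protocol's primary hypothesis. The Change Process Capability Questionnaire and the acceptability, appropriateness and feasibility surveys do not pass through this route.

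**Working it through.** No arithmetic applies. The documents do not count inclusion decisions, and the point rests on roles, timing and masking. The steps below set the texts side by side.

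1. **Whose data, and who decides.** In Protocol section 9 the collaborator is named for chart audits, the weekly-meeting sentence follows at once, and surveys come afterwards as a separate topic. The natural reading is that the facilitator attends the meetings and that the data in question are chart-audit data. Because names are removed, this is a reading and not a certainty. The protocol does not define included data: it could mean whole charts, data elements or single values. No rule or log for the decisions is given.

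2. **Are the decisions made after allocation?** Randomisation is in Year 1, quarter 1. The follow-up audit comes after the intervention. The protocol's inclusion criteria also require a visit after the intervention start, so the eligible list cannot be completed before allocation. The status of the baseline audit is less clear, because the text describes it as pre-intervention while the protocol's timeline table, as extracted, marks chart audits only in Year 2. At least the follow-up decisions come after arm is known.

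3. **Is it the same role, and the same person?** The job title matches between Protocol section 9 and SAP Table 1. The Setting paragraph implies several facilitators across the network, and says that they collect research data as well as support improvement. The title match therefore shows a possible overlap of duties, not one person holding both.

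4. **Is anyone masked?** The text available states no masking to arm for the facilitator, abstractors, quantitative team or analysts. The opening text of both documents was not available, so this is a statement about the rest. Removing patient identifiers, which the protocol does plan, does not conceal the arm.

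5. **Do the listed safeguards close the route?** Random selection protects the draw of charts but not what happens to a chart once drawn. The abstraction protocol and training narrow discretion. Kappa compares one abstractor with another: two abstractors can agree fully on a record that a meeting later sets aside. The mixed models, with or without covariates, see only the data that survive the decisions, so they cannot correct a differential inclusion made beforehand.

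**The case against.** The strongest reply is that the conflict is inferred from a job title. A reader might conclude that the person who delivered INTEGRATE-D chose which charts counted. The documents do not support that. The subject of the key sentence is a removed name, the network has more than one facilitator, and collecting research data is an ordinary part of the post. The SAP, written after the event, assigns the EHR work to research, clinic and audit staff and mentions no such part for the facilitator. This stands, and it limits the point to a conditional one. It does not dispose of it, because the SAP neither withdraws the protocol's sentence nor says who made inclusion decisions.

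Two further replies have weight. First, the quantitative team is not shown to be masked either, so moving decisions to it helps only if labels are stripped. Second, the study is a four-practice pilot that the protocol itself describes as not suited to conclusive evidence of effectiveness, and the data have been collected. Both bear on how much to ask for. The protocol also looks ahead to a larger trial, which could inherit the arrangement.

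**Conclusion.** The point holds in conditional form, as a minor and cheaply avoidable weakness. The protocol, on its natural reading, puts a practice facilitator into chart-data inclusion decisions made after randomisation, and no masking is described. If that facilitator worked with an intervention clinic, arm-aware decisions were possible, and nothing in the stated safeguards or analysis would reveal or undo them.

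The size of any bias is unknown. It is probably small, because charts are drawn at random, abstraction follows a protocol and is partly automated, decisions are shared with the quantitative team, and most measures are objective laboratory or screening records. A reader might infer that the chart results are biased, or biased in favour of the intervention. Nothing in the documents shows that even one record was included or excluded by discretion, so neither inference is supported.

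The conclusion assumes that the two adjacent sentences in Protocol section 9 concern the same person and the chart-audit data, and that the unavailable opening text contains no masking statement.

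**What to change.** Amend the Data Security text of Protocol section 9 so that anyone who facilitates an intervention clinic may answer questions about where data sit in the EHR, but takes no part in inclusion decisions. The existing quantitative team, including the biostatistician who already manages the chart data, should decide against the standard abstraction protocol. It should work from query lists with clinic and arm labels removed where feasible, and lock its decisions before arm is joined to the data.

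For data already collected, state in the SAP or the report what the included-data decisions covered, who made them, and whether those people knew the arm. If the facilitator had no part, or did not work with an intervention clinic, one sentence saying so settles the matter.

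The cost is some wording, label removal on query lists and a short reporting statement, all by staff already in place. Clinic-specific EHR questions may take longer to resolve. Masking will be imperfect: there are only four clinics, and diabetes distress screening, which the SAP attributes to the intervention clinics, can reveal the arm.
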